### **12.2 Other Response Parameters**

Participants' medical records will be used to assess the development of severe respiratory or other organ failure in the study population at 40 days, as well as to assess mortality and rate of severe adverse events defined as grade 3 non hematologic or greater by DMID Toxicity Scale for Determining Severity of Adverse Events.

Safety, tolerability and compliance with of each regimen will be recorded on case report forms.

## **13. STUDY APPROVAL, OVERSIGHT AND DATA REPORTING / REGULATORY REQUIREMENTS**

### **13.1 Protocol Review and Monitoring Committee and Institutional Review Board Review**

Before implementing this study, the protocol must be reviewed by the Markey Cancer Center's Protocol Review and Monitoring Committee and the protocol, the proposed informed consent form and other information to subjects, must be reviewed by the University of Kentucky Institutional Review Board (IRB). A signed and dated UK IRB initial review approval memo must be maintained in the Markey Cancer Center Clinical Research Office (MCC CRO) regulatory binder. Any amendments to the protocol, other than administrative ones, must be reviewed and approved by the PRMC, study sponsor and the UK IRB.

### **13.2 Quality Assurance**

The MCC places the highest priority on ensuring the safety of subjects participating in clinical trials and on the quality of data obtained from clinical and translation research. The MCC Quality Assurance (QA) Office oversees the maintenance of quality standards in clinical cancer research through clinical data monitoring of Investigator-Initiated Trials (IITs) and routine audits.

#### **13.2.1 Data Monitoring**

The MCC QA Office will collaborate with the PI, Biostatisticians and Data Management Specialist in creating a Clinical Data Monitoring Plan (CDMP) using a risk-based approach. The CDMP will

describe the scope, communication plan, and frequency of monitoring visits. In addition, describe query submissions and resolutions, action items and monitoring reports.

The QA monitor assigned to the trial will perform the monitoring tasks in accordance with the protocol-specific CDMP. The monitoring process will provide research staff and the PI with the opportunity to evaluate the progress of the study, verify the accuracy and completeness of the case report forms, assure that all protocol requirements, including applicable regulations and investigator's obligations are being fulfilled, and prompt resolution of any inconsistencies in the study records.

### 13.2.2 Audit

To ensure compliance with the International Conference on Harmonisation of Good Clinical Practice Guidelines and all applicable regulatory requirements, the MCC Audit Committee will conduct a quality assurance audit. A minimum of 10% of patients enrolled in the study may be selected for review. The purpose of a MCC audit is to systematically and independently examine all study-related activities and documents to determine whether these activities were conducted, and data were recorded, analyzed, and accurately reported according to the protocol, Good Clinical Practice guidelines of the International Conference on Harmonization, and any applicable regulatory requirements.

## 13.3 Data and Safety Monitoring Committee

The MCC Data and Safety Monitoring Committee (DSMC) will oversee the conduct of this trial. The MCC DSMC performs routine real-time data monitoring and safety review of all trials, with a special focus upon investigator-initiated trials (IITs). The MCC DSMC will conduct review of the trial on a schedule determined by the MCC Protocol Review & Monitoring Committee (PRMC).

The MCC DSMC will monitor the following elements of the trial: adverse event analysis, serious adverse events, protocol deviations/violations, and accrual. In addition, when applicable the DSMC will review QA audits and monitoring reports, previous reviews by the DSMC, suggested actions by other committees (such as the IRB, UK Risk Management Committee), and other parameters and outcomes as determined by the DSMC. If appropriate, the DSMC will designate and monitor corrective action(s) based on review outcome. The MCC DSMC has the authority to amend, temporarily suspend, or terminate the trial based upon patient safety or compliance matters.

Adverse event lists, guidelines, and instructions for AE reporting can be found in Section 10.0 (Adverse Events: List and Reporting Requirements).

## 13.4 Data Reporting

### 13.4.1 Method

This study will require minimal data set submission and reporting via the OnCore Enterprise Research Clinical Trials Management System. Case report forms will be created in a RedCap

database. Instructions for submitting data is listed in study-specific guidance documents. These guidance documents may include any of the following, as appropriate for the scope of the study: eCRF Completion Guidelines, Data Management Specifications, Subject Console Guide, and Query Resolution Guide.

#### **13.4.2 Responsibility for Data Submission**

This trial will be monitored by the MCC Data and Safety Monitoring Committee (DSMC) on a schedule determined by the Protocol Review and Monitoring Committee at the initial PRMC review. Study staff are responsible for submitting study data and/or data forms as per the Markey Cancer Center SOPs. Study staff are responsible for compiling and submitting data for all participants and for providing the data to the Principal Investigator for review.

### **13.5 Data Management**

Data management will be performed by cross-team members at MCC. These team members will include representatives from the Biostatistics and Bioinformatics SRF, and the Quality Assurance Office. They will work closely with study staff to ensure timely and accurate data submission. A protocol-specific Data Management Plan (DMP) will be authored by the biostatistician and Principal Investigator with each expected to review and approve the finalization of the DMP. In order to maintain best clinical practices in data management, the DMP may include, but not be limited to: CRF/eCRF design, database build and design, database training, edit check/validation specifications, study database testing/release, data and paper workflow, report, metrics, query/discrepancy management, management of external (including lab) data, medical coding, SAE handling/reconciliation, data transfers and database lock. The protocol-specific DMP will additionally define the schedule at which data will be accessed by data management and study statistician to perform statistical programming for conduct of data quality, data control, data management, generation of interim reports and statistical analysis. Cross-team members will collaborate to establish procedures and timelines for quality control, audits, query resolution, annual reports, interim analysis and final data analysis.

### **13.6 Compliance with Laws and Regulations**

The study will be conducted in accordance with U.S. Food and Drug Administration (FDA) and International Conference on Harmonization (ICH) Guidelines for Good Clinical Practice (GCP), the Declaration of Helsinki, any applicable local health authority, and Institutional Review Board (IRB) requirements. The PI or designee will be responsible for obtaining continuing and not less than annual IRB re-approval throughout the duration of the study. Copies of the Investigator's annual report to the IRB and copies of the IRB continuance of approval must maintained by the MCC CRO. The PI or designee is also responsible for notifying the Data and Safety Monitoring Committee of the MCC and the UK IRB of any significant adverse events that are serious and/or unexpected, as per SOP's of those entities and compliance with protocol requirements. DSMC will review all adverse events of this IIT as per its SOP.

**APPENDIX A: OBESITY SCALE**

HEIGHT	WEIGHT (lbs.)																												
	130	140	150	160	170	180	190	200	210	220	230	240	250	260	270	280	290	300	310	320	330	340	350	360	370	380	390		
5'0"	25	27	29	31	33	35	37	39	41	43	45	47	49	51	53	55	57	59	61	62	64	66	68	70	72	74	76		
5'1"	25	26	28	30	32	34	36	38	40	42	43	45	47	49	51	53	55	57	59	60	62	64	66	68	70	72	74		
5'2"	24	26	27	29	31	33	35	37	38	40	42	44	46	48	49	51	53	55	57	59	60	62	64	66	68	70	71		
5'3"	23	25	27	28	30	32	34	35	37	39	41	43	44	46	48	50	51	53	55	57	58	60	62	64	66	67	69		
5'4"	22	24	26	27	29	31	33	34	36	38	39	41	43	45	46	48	50	51	53	55	57	58	60	62	64	65	67		
5'5"	22	23	25	27	28	30	32	33	35	37	38	40	42	43	45	47	48	50	52	53	55	57	58	60	62	63	65		
5'6"	21	23	24	26	27	29	31	32	34	36	37	39	40	42	44	45	47	48	50	52	53	55	56	58	60	61	63		
5'7"	20	22	23	25	27	28	30	31	33	34	36	38	39	41	42	44	45	47	49	50	52	53	55	56	58	60	61		
5'8"	20	21	23	24	26	27	29	30	32	33	35	36	38	40	41	43	44	46	47	49	50	52	53	55	56	58	59		
5'9"	19	21	22	24	25	27	28	30	31	32	34	35	37	38	40	41	43	44	46	47	49	50	52	53	55	56	58		
5'10"	19	20	22	23	24	26	27	29	30	32	33	34	36	37	39	40	42	43	44	46	47	49	50	52	53	55	56		
5'11"	18	20	21	22	24	25	26	28	29	31	32	33	35	36	38	39	40	42	43	45	46	47	49	50	52	53	54		
6'0"	18	19	20	22	23	24	26	27	28	30	31	33	34	35	37	38	39	41	42	43	45	46	47	49	50	52	53		
6'1"	17	18	20	21	22	24	25	26	28	29	30	32	33	34	36	37	38	40	41	42	44	45	46	47	49	50	51		
6'2"	17	18	19	21	22	23	24	26	27	28	30	31	32	33	35	36	37	39	40	41	42	44	45	46	48	49	50		
6'3"	16	17	19	20	21	22	24	25	26	27	29	30	31	32	34	35	36	37	39	40	41	42	44	45	46	47	49		
6'4"	16	17	18	19	21	22	23	24	26	27	28	29	30	32	33	34	35	37	38	39	40	41	43	44	45	46	47		

**BMI**

<19	Underweight
19-25	Healthy weight
26-29	Overweight
30-39	Obese
>40	Morbid Obesity

**APPENDIX B: COVID 7-POINT ORDINAL OUTCOMES SCALE**

<http://www.who.int/blueprint/priority-diseases/key-action/novel-coronavirus/en/>

**COVID 7-point ordinal outcomes scale:**

1. Death
2. Hospitalized on invasive mechanical ventilation or ECMO
3. Hospitalized on non-invasive ventilation or high flow nasal cannula
4. Hospitalized on supplemental oxygen
5. Hospitalized not on supplemental oxygen
6. Not hospitalized with limitation in activity (continued symptoms)
7. Not hospitalized without limitation in activity (no symptoms)

*IMP: Artemisia annua, Artesunate, Camostat mesilate, Ivermectin,  
Study #: MCC-20-COVID-01-PMC  
Amendment 4 August 28, 2020*

## **APPENDIX C: PILL/PRODUCT DIARIES**

### Study Participant Self-Administration Study Drug Diary

Please record how many tablets you take, the time you take them and any comments below and bring the completed Diary as well as your study drug supply, including empty bottles, to every study visit. This will help us keep track of your study drug and how well you are tolerating it.

#### Arm C

Participant Identifier:	Protocol #: MCC-20-COVID-01-PMC
Doctor: [name] [name]	
Doctor: [name] [name]	
Nurse: enter name and phone number	

You will take the following number of capsules/tablets each time (per dose) as listed in the table below:

Study Drug Name	# of capsules (tablets) to take per time/dose	# of times/doses each day	Approximate time to take drug
Ivermectin	__ tablets/12mg-15mg (circle one)	Once a day 2 hours before or 2 hours after a meal	__:__  a.m.

Day	Date	Number of Ivermectin Tablets	Time of Dose
1		—	__:__  a.m.  Dose Not Taken Why:
2		—	__:__  a.m.  Dose Not Taken Why:

Participant/Caregiver Signature: \_\_\_\_\_

Date: \_\_\_\_\_

FOR STUDY TEAM USE ONLY	
Staff Initials:	
Date Dispensed:	Date Returned:
# pills/caps/tabs dispensed:	# pills/caps/tabs returned:
# pills/caps/tabs that should have been taken:	
Discrepancy Notes:	

*IMP: Artemisia annua, Artesunate, Camostat mesilate, Ivermectin,  
Study #: MCC-20-COVID-01-PMC  
Amendment 4 August 28, 2020*

### Study Participant Self-Administration Study Drug Diary

Please record how many tablets you take, the time you take them and any comments below and bring the completed Diary as well as your study drug supply, including empty bottles, to every study visit. This will help us keep track of your study drug and how well you are tolerating it.

#### Arm D

Participant Identifier:	Protocol #: MCC-20-COVID-01-PMC		
Doctor: [name] [name]			
Doctor: [name] [name]			
Nurse: enter name and phone number			
You will take the following number of capsules/tablets each time (per dose) as listed in the table below:			
Study Drug Name	# of capsules (tablets) to take per time/dose	# of times/doses each day	Approximate time to take drug
Camostat Mesilate	2 tablets	3 times per day	___:___  a.m. ___:___  p.m. :  p.m.

Day	Date	Number of Camostat Mesilate 100 mg	Time of Dose	Number of Camostat Mesilate 100 mg	Time of Dose	Number of Camostat Mesilate tablets	Time of Dose
1		2	___:___  a.m.  Dose not taken Why: _____	2	___:___  p.m.  Dose not taken Why: _____	2	___:___  p.m.  Dose not taken Why: _____
2		2	___:___  a.m.  Dose not taken Why: _____	2	___:___  p.m.  Dose not taken Why: _____	2	___:___  p.m.  Dose not taken Why: _____
3		2	___:___  a.m.  Dose not taken Why: _____	2	___:___  p.m.  Dose not taken Why: _____	2	___:___  p.m.  Dose not taken Why: _____
4		2	___:___  a.m.  Dose not taken Why: _____	2	___:___  p.m.  Dose not taken Why: _____	2	___:___  p.m.  Dose not taken Why: _____
5		2	___:___  a.m.	2	___:___  p.m.	2	___:___  p.m.

			 Dose not taken Why: _____		 Dose not taken Why: _____		 Dose not taken Why: _____
6		2	____:____  a.m.  Dose not taken Why: _____	2	____:____  p.m.  Dose not taken Why: _____	2	____:____  p.m.  Dose not taken Why: _____
7		2	____:____  a.m.  Dose not taken Why: _____	2	____:____  p.m.  Dose not taken Why: _____	2	____:____  p.m.  Dose not taken Why: _____
8		2	____:____  a.m.  Dose not taken Why: _____	2	____:____  p.m.  Dose not taken Why: _____	2	____:____  p.m.  Dose not taken Why: _____
9		2	____:____  a.m.  Dose not taken Why: _____	2	____:____  p.m.  Dose not taken Why: _____	2	____:____  p.m.  Dose not taken Why: _____
10		2	____:____  a.m.  Dose not taken Why: _____	2	____:____  p.m.  Dose not taken Why: _____	2	____:____  p.m.  Dose not taken Why: _____
11		2	____:____  a.m.  Dose not taken Why: _____	2	____:____  p.m.  Dose not taken Why: _____	2	____:____  p.m.  Dose not taken Why: _____
12		2	____:____  a.m.  Dose not taken Why: _____	2	____:____  p.m.  Dose not taken Why: _____	2	____:____  p.m.  Dose not taken Why: _____
13		2	____:____  a.m.  Dose not taken Why: _____	2	____:____  p.m.  Dose not taken Why: _____	2	____:____  p.m.  Dose not taken Why: _____
14		2	____:____  a.m.  Dose not taken Why: _____	2	____:____  p.m.  Dose not taken Why: _____	2	____:____  p.m.  Dose not taken Why: _____

Participant/Caregiver Signature: \_\_\_\_\_  
 Date: \_\_\_\_\_

*IMP: Artemisia annua, Artesunate, Camostat mesilate, Ivermectin,  
Study #: MCC-20-COVID-01-PMC  
Amendment 4 August 28, 2020*

FOR STUDY TEAM USE ONLY	
Staff Initials:	
Date Dispensed:	Date Returned:
# pills/caps/tabs dispensed:	# pills/caps/tabs returned:
# pills/caps/tabs that should have been taken:	
Discrepancy Notes:	

### Study Participant Self-Administration Study Botanical Diary

Please record the number of times you drink the *Artemisia annua* tea or coffee, the time you take them and any comments below and bring the completed Diary as well as your study tea or coffee supply, to your next study visit. This will help us keep track of your study product and how well you are tolerating it.

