### **1.2 Secondary Objectives**

- 1.2.1 To assess the decrease in viral load at Day 14.
- 1.2.2 To assess the development of severe respiratory or other organ failure in the study population
- 1.2.3 To assess progression to ICU care or ventilation in non-critically ill hospitalized patients and overall study population
- 1.2.4 To assess clearance of viral RNA by PCR testing at days 1, 14, 28, and 40 days
- 1.2.5 To assess mortality, clinical status of subject at Day 14, using the COVID 7-point ordinal outcomes scale, and rate of severe adverse events defined as grade 3 non hematologic or greater by DMID Toxicity Scale for Determining Severity of Adverse Events
- 1.2.6 To assess the safety, tolerability and compliance with each regimen.

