#### 6.1 Agent Administration

The CURE Alliance Drug Steering Committee will serve as the drug selection committee to identify the appropriate new drugs for each new arm of this clinical trial. Treatment will be administered on an outpatient or inpatient basis provided that entry criteria are met. If emerging data indicates futility of a medication in one or more arms of our study, and was tested in a similar patient population in a randomized clinical trial or trials, the study drug selection committee may recommend removal of that drug treatment arm for futility with approval of the study team. Once a futility endpoint is met in an arm, we will replace that arm with the next appropriate proposed arm with approval of the CURE Alliance Drug Steering Committee. **All subjects receive standard supportive treatment throughout their infection, whether outpatient or during inpatient hospitalization.** Reported adverse events and potential risks are described in Section 10.

Treatment regimens will be evaluated and novel agents selected by the steering committee. Should drug supply become unavailable that arm would pause until drug supply is available.

Regimen Description- Arm C				
Agent	Formulation Strength	Daily Dose	Route	Schedule
Ivermectin	3 mg tablet	12-15 mg	Oral	Weight < 75kg: 4 tabs on Days 1 and 2, (12 mg total daily dose) Weight ≥ 75kg: 5 tabs on Days 1 and 2, (15 mg total daily dose)

Regimen Description- Arm D				
Agent	Formulation Strength	Daily Dose	Route	Schedule
Camostat Mesilate	100 mg tablet	600mg	Oral	2 tab TID after a meal (600 mg total daily dose) Days 1-14

Regimen Description- Arm E				
Agent	Formulation Strength	Daily Dose	Route	Schedule
Artemisia annua tea or coffee	Decaf coffee 450mg per pod Tea 225mg per bag	1350 mg	Oral	One 8oz brewed tea (two bags) or one coffee pod TID Days 1-14

Regimen Description- Arm F				
Agent	Formulation Strength	Daily Dose	Route	Schedule
Artesunate	100mg	200mg	Oral	Two tabs once day (200mg total) Days 1-14

Patients will be assigned to a treatment arm according to the randomization process described in Section 9 of this protocol

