#### 8.1.5 *Artemisia annua* tea and coffee

### Procurement

**Outpatients:** Coffee and tea botanical products will be directly shipped overnight to study patients, who are outpatients by Baesman on behalf of ArtemiLife. Patients without a pod coffee maker will also receive a coffee maker.

The distributor for *Artemisia annua* is as follows:

Baesman Distributors

[name]

[name]

Contact: [[contact]](mailto:[contact])

Subjects randomized to Arm E will have their information entered into the ordering portal of

*IMP: Artemisia annua, Artesunate, Camostat mesilate, Ivermectin,  
Study #: MCC-20-COVID-01-PMC  
Amendment 4 August 28, 2020*

Baesman Distributors website.

**Inpatients:** This botanical product will be dispensed by Artemilife to the IDS pharmacy.

Formulation

Decaf coffee: 450 mg per pod

Tea: 225 mg per bad

Preparation, Storage and Stability

Tea and coffee should be stored at room temperature.

Coffee: Dispense 42, 450 mg pods

Tea: Dispense 84, 225 mg bags

Administration

Refer to the treatment section for specific administration instructions

Patients should be instructed to brew 1 (450mg) coffee pod or 2 (225mg) tea bags in 8 oz of water three times per day Days 1-14.

Drug Interactions

Increased Effect/Toxicity: No known drug interactions

Decreased Effect: CYP2A6 strong inducers may reduce the effects of Artemisia annua

Herb/Nutraceutical Interactions: No known interactions

Pharmacokinetics

Absorption: well absorbed orally

Distribution: Not established

Metabolism: Metabolized by CYP2A6

Half-life elimination: 1hr

Terminal: Not reported

Excretion: Not known

Adverse Events

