#### Arm E

Participant Identifier:	Protocol #: MCC-20-COVID-01-PMC		
Doctor: [name] [name]			
Doctor: [name] [name]			
Nurse: enter name and phone number			
You will take the following number of capsules/tablets each time (per dose) as listed in the table below:			
Study Botanical Product Name	dose	# of times/doses each day	Approximate time to take tea or coffee
Artemisia annua	1 pod or 2 tea bags	3 times per day	___:___  a.m. ___:___  p.m. :  p.m.

Day	Date	Number of Artemisia annua tea bag or pod	Time of Dose	Number of Artemisia annua tea bag or pod	Time of Dose	Number of Artemisia annua tea bag or pod	Time of Dose
1		-	___:___  a.m.  Dose not taken Why: _____	-	___:___  p.m.  Dose not taken Why: _____	-	___:___  p.m.  Dose not taken Why: _____
2		-	___:___  a.m.  Dose not taken Why: _____	-	___:___  p.m.  Dose not taken Why: _____	-	___:___  p.m.  Dose not taken Why: _____
3		-	___:___  a.m.  Dose not taken Why: _____	-	___:___  p.m.  Dose not taken Why: _____	-	___:___  p.m.  Dose not taken Why: _____
4		-	___:___  a.m.  Dose not taken Why: _____	-	___:___  p.m.  Dose not taken Why: _____	-	___:___  p.m.  Dose not taken Why: _____

5		-	____:____  a.m.  Dose not taken Why: _____	-	____:____  p.m.  Dose not taken Why: _____	-	____:____  p.m.  Dose not taken Why: _____
6		-	____:____  a.m.  Dose not taken Why: _____	-	____:____  p.m.  Dose not taken Why: _____	-	____:____  p.m.  Dose not taken Why: _____

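### The unit counts in the Arm D and Arm E diaries are unreliable for partial doses, so compliance with those regimens is measured less accurately than intended

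*Combined protocol and SAP*

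**What the plan says.** Section 1.2.6 sets the objective: "To assess the safety, tolerability and compliance with each regimen". Section 12.2 adds that compliance goes on case report forms. Neither gives a formula, and sections 9.2 and 9.5 list no compliance analysis.

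Arm E diary (Appendix C):
- The instruction opens "Please record the number of times you drink the" and goes on to name the tea or coffee. It asks for occasions.
- The table column is headed "Number of Artemisia annua tea bag or pod". It asks for units, and its cells are blank.
- The stated dose is "1 pod or 2 tea bags", three times per day. The diary has no field for which product was used, and the staff block is labelled for pills, capsules and tablets.

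Arm D diary (Appendix C):
- The instruction is "Please record how many tablets you take, the time you take them and any comments below".
- The count columns, for example "Number of Camostat Mesilate 100 mg", already carry a printed 2 at each of three doses on each of 14 days.
- Section 6.1 gives the schedule as "2 tab TID after a meal (600 mg total daily dose) Days 1-14", and section 8.1.4 repeats the meal condition. The diary does not carry it.

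Both diaries have a time of dose and a missed-dose box with a reason at every slot. Both have a staff block for units dispensed, returned and expected. Section 4.9 has medications and diaries collected at Day 14.

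**The concern.** The count column is the only diary field that can show a dose taken in part. In Arm E it can be filled in on two scales, and for tea users these differ by a factor of two. In Arm D it is filled in before the patient starts, so it reports a full dose by default at every slot where a dose was taken.

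What is at stake is the accuracy of the compliance figure for these two regimens. If a regimen looks weak at the end of the trial, a reader will want to know whether patients took it as scheduled. In these two arms the diary count cannot answer that at the level of single doses.

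**Working it through.** **Inputs.** Treatment runs for 14 days with three doses per day in Arms D and E (section 6.1). A dose is 2 tablets in Arm D, and 1 pod or 2 bags in Arm E. The amounts dispensed are 84 tablets (section 8.1.4), and 42 pods or 84 bags (section 8.1.5 and the Appendix H order form). The coffee entry reads "Coffee: Dispense 42, 450 mg pods".

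**Reproducing the plan's figures.** Slots = 14 × 3 = 42.
- Arm D: 42 × 2 = 84 tablets.
- Arm E coffee: 42 × 1 = 42 pods.
- Arm E tea: 42 × 2 = 84 bags.

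All three agree with the amounts dispensed, so these are the right denominators.

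**Arm E, an entry of 1 in all 42 cells.**
- Read as occasions or as pods: 42/42 = 100%.
- Read as tea bags: 42/84 = 50%.

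A tea user who followed the instruction and used 84 bags leaves the same column as one who followed the heading and used 42. Knowing from the order form that the patient received tea does not settle which was meant. Knowing the product does settle an entry of 2: it is 84/84 = 100% for bags, and would be 84/42 = 200% for pods.

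**Arm D, one tablet instead of two at h slots.** The unaltered diary shows 84/84 = 100% whatever h is. Tablets actually taken are (84 − h)/84:

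| h | Printed diary | Tablets taken |
|---|---|---|
| 7 | 100% | 77/84 = 91.7% |
| 14 | 100% | 70/84 = 83.3% |
| 42 | 100% | 42/84 = 50.0% |

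**What the other fields recover.** Whole missed doses are visible in both arms on one scale. Seven missed doses give 35/42 = 83.3%, and should match 14 returned tablets, 7 pods or 14 bags. The two tea users above would return 0 and 42 bags, so a complete return count separates them in total. Neither field shows which doses were partial: the box is yes or no, and the return count is a sum over the whole course.

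**Arm-level bound for Arm E.** The documents do not give the share s of patients choosing tea. Suppose every patient is fully adherent, every tea user writes 1 per dose, every such entry is read as one bag, and returns are ignored. The arm would then be summarised as 1 − 0.5s: 87.5% at s = 25%, 75% at s = 50%, and 62.5% at s = 75%. This is a worst case, not an expected error.

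**The case against.** A reader might infer that compliance cannot be measured in these arms, or cannot be compared between them. The documents do not support that. Each of the 42 slots has its own time and missed-dose box, so doses taken out of 42 can be computed in both arms without the count column. Arm D does not default to full compliance for missed doses. Patients are told to bring their supply back, staff record dispensed and returned counts with discrepancy notes, and the order form shows which Arm E product was sent. The arm-level bound above needs staff to ignore all of that. Section 9.1 also says that comparisons between arms are not part of this design, so a distorted between-arm compliance contrast is a harm to an analysis nobody has planned. Printing a fixed dose beside a missed-dose box can be defended as a matter of form style.

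Most of this stands and limits the point to partial doses. Three things remain. The box cannot record a partial dose. The return count depends on patients bringing product back, and section 8.1.2 makes the Arm E product an exception to the usual drug accountability practice, so the check is weakest where the diary is most ambiguous. And with no compliance formula, nothing says which field prevails when they disagree.

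The missing meal condition in the Arm D diary is an omission, not a contradiction, and does not affect the counts. Section 8.1.4 says patients are to be instructed on it, and section 4.9 has instructions handed out on Day 1. It is a minor point of consistency.

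**Conclusion.** The point holds for partial doses only. In Arm E, a tea user's 42 entries of 1 fit either 100% or 50% of the expected bags. In Arm D, partial dosing leaves the printed count at 100% while true intake could be as low as 50% with one tablet at every slot. Both statements describe what the forms permit. How often patients take partial doses, and how many choose tea, is not in the documents.

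Compliance with each regimen remains measurable from missed doses out of 42 and, where product comes back, from a return total. It is less accurate than section 1.2.6 intends. The primary endpoint, the sample size and the interim rules do not depend on it. This is a modest defect of form design that is worth correcting because the correction is so cheap.

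**What to change.** Arm E diary:
- Add one tick for the product, pods or bags.
- Make the instruction and the column heading both ask for the number of pods or bags used at that dose.
- Relabel the staff block in pods or bags, with 42 or 84 expected.

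Arm D diary:
- Replace each printed 2 with a blank for the patient to fill in.
- Reconcile the diary with sections 6.1 and 8.1.4 on the meal condition.

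It would also help to state in section 12.2 or 9.5 how compliance is computed (units used divided by 84 tablets, 42 pods or 84 bags, with doses taken out of 42 alongside) and which source prevails when diary and return count differ.

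The cost is a revision of two patient forms and, if adopted, one added sentence in the plan. No extra visits, samples or patients are needed.

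A separate matter in the same appendix could go into the same revision. The Arm F diary describes artesunate in pods and tea bags three times per day, while sections 6.1 and 8.1.6 describe tablets once a day. Those passages contradict each other and must be reconciled.
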